#### **8.4 Safety Follow-Up Visit (20 weeks [-3 days/+7 days] after the final dose)**

All subjects who complete the study and do not enter the extension study or who discontinue early, including those withdrawn from IMP, will have an SFU Visit 20 weeks after their final dose of IMP with the following assessments:

- Record concomitant medications
- PHQ-9
- eC-SSRS
- Weight
- Vital signs
- ECG by central reader
- Collect samples for hematology/biochemistry
- Collect samples for hs-CRP
- Pregnancy testing (urine)
- Urinalysis
- Blood sample for bimekizumab plasma concentrations
- Blood sample for anti-bimekizumab antibody detection
- TB questionnaire
- Physical examination

- BSA affected by PSO
- PASI (if BSA affected by PSO is  $\geq 3\%$  at the Baseline [Day 1] visit)
- IGA
- Perform TJC and SJC
- HAQ-DI
- PtAAP
- PhGA-PsA
- PhGA-Arthritis
- PGA-PsA
- PGA-Arthritis
- BASDAI
- LEI
- SPARCC
- LDI
- PsAQoL
- SF-36
- AEs
- IXRS

## **8.5            Unscheduled Visits**

At the Investigator's discretion, an Unscheduled Visit may be completed at any time during the study but prior to the SFU Visit, if deemed necessary for the subject's safety and wellbeing.

If an Unscheduled Visit is conducted due to safety or efficacy reasons, an eC-SSRS assessment will be performed with the subject during the visit. If an Unscheduled Visit is conducted for reasons other than safety or efficacy concerns (eg, replacement of lost medication, repeated collection of a laboratory specimen due to collection or analysis issues), an eC-SSRS will not be required at these visits.

At this visit, any of the following assessments may be performed, depending on the reason for the visit:

- Record concomitant medication
- eC-SSRS
- Vital signs
- ECG
- Obtain urine sample for urine pregnancy test

- If indicated, obtain blood sample(s) for:
  - Standard safety laboratory tests (hematology/biochemistry)
  - Bimekizumab plasma concentrations and anti-bimekizumab antibody detection
- An IGRA TB test
- Physical examination
- AEs

## **9 ASSESSMENT OF EFFICACY**

The ACR50 response at Week 16 is the primary efficacy variable. In addition, the ACR20 and ACR70 responses are secondary or other efficacy variables. Several assessments must be completed in order to determine the ACR response. These include the TJC and SJC based on 68 and 66 joints, respectively, PGA-PsA, PhGA-PsA, PtAAP, HAQ-DI and hs-CRP. The methods for the component measures will be described first, followed by ACR response and assessments used in secondary and other efficacy variables.

The timing for all assessments is specified in the schedule of study assessments ([Table 5-1](#)).

### **9.1 Joint assessments**

#### **9.1.1 68/66 joint evaluation for ACR response and verification of Inclusion Criterion 5**

The TJC/SJC, as recommended by ACR in RA, is the 68/66 count and it has since also been used in PsA studies; therefore, it will be utilized in this study.

All joint assessments will be performed by an experienced independent evaluator who has had documented training on how to perform these assessments correctly. Preferably, the same evaluator should perform these assessment at all visits, as indicated in [Table 5-1](#). The independent evaluator will not be involved in any other assessments. The following joints will be assessed for tenderness:

- Upper body (6) - bilateral temporomandibular, sternoclavicular, and acromioclavicular joints
- Upper extremity (34) - bilateral shoulders, elbows, wrists (includes radiocarpal, and carpal and carpometacarpal bones considered as a single unit), metacarpophalangeal (I, II, III, IV, and V), thumb interphalangeals, proximal interphalangeal (II, III, IV, and V), and distal interphalangeals (II, III, IV, and V).
- Lower extremity (28) - bilateral hips, knees, ankles, tarsi (includes subtalar, transverse tarsal, and tarsometatarsal considered as a single unit), metatarsophalangeals (I, II, III, IV, and V), great toe interphalangeals, and proximal interphalangeals (II, III, IV, and V).

All of these except for the hips are assessed for swelling.

Artificial and ankylosed joints, as well as missing joints (ie, amputated joints), are excluded from both tenderness and swelling assessments.

One dactylitic digit is to be counted as 1 swollen joint (instead of counting as 3 in the finger or 2 in the toe).

**Table 9-1** summarizes the swelling and tenderness grading criteria.

### **Table 9-1: Swelling and tenderness grading**

Grade	Tenderness response (68)	Swelling response (66)
0	Not tender	None
1	Tenderness present	Detectable synovial thickening

Data mapping from collected data to the grades listed in [Table 9-1](#) will be described in the Statistical Analysis Plan (SAP).

### **9.1.2 28 joint evaluation for determination of DAS28(CRP)**

The following 28 joints will be used for calculation of the DAS28(CRP).

- Upper extremity (26)-bilateral shoulders, elbows, wrists (includes radiocarpal, and carpal and carpometacarpal bones considered as a single unit), metacarpophalangeal joints I, II, III, IV, and V, thumb interphalangeals, proximal interphalangeal II, III, IV, and V
- Lower extremity (2)-knees

### **9.2 ACR20, ACR50, and ACR70 response**

The ACR20, ACR50, and ACR70 response rates are based on a 20%, 50%, and 70% or greater improvement relative to Baseline in the following measures:

- TJC based on 68 joints
- SJC based on 66 joints
- 3 of the 5 remaining core set measures:
  - PGA-PsA
  - PhGA-PsA
  - PtAAP
  - HAQ-DI
  - hs-CRP

### **9.3 Patient's Global Assessments**

#### **9.3.1 Patient's Global Assessment of Psoriatic Arthritis (PGA-PsA)**

The subject's global assessment of PsA will be performed using a 100mm VAS scale where 0 is "very good, no symptoms" and 100 is "very poor, severe symptoms." The subject will be asked the following question:

**"Considering all the ways your psoriatic arthritis affects you, please mark a vertical line on the scale below to show how well you are doing today."**

The subject should be asked to consider all aspects of their disease (including joint and skin components) in their response to this question.

### **9.3.2 Patient's Global Assessment of Arthritis (PGA-arthritis)**

The subject's global assessment of arthritis will be performed using a 100mm VAS scale where 0 is "very good, no symptoms" and 100 is "very poor, severe symptoms." The subject will be asked the following question:

**"Considering all the ways your arthritis affects you, please mark a vertical line on the scale below to show how you are feeling today."**

The subject should be asked to consider their arthritis symptoms and functional capacity in their response to this question.

## **9.4 Physician's Global Assessments**

These assessments will be performed by the Principal Investigator, another delegated physician or an appropriately trained medical professional (based on local requirements) who has documented training on how to perform these assessments correctly. The assessments should be made blind to the PGA-PsA and PGA-Arthritis assessments.

### **9.4.1 Physician's Global Assessment of Psoriatic Arthritis (PhGA-PsA)**

The Investigator or delegate will assess the overall status of the subject with respect to their PsA, which may include any element of the disease and may include arthritis, PSO, enthesitis, dactylitis, or spondylitis. This will be assessed using a 100mm VAS scale where 0 is "very good, asymptomatic and no limitation of normal activities" and 100 is "very poor, very severe symptoms which are intolerable and inability to carry out all normal activities". The Investigator or delegate will be asked the following question:

**"Considering all the ways the disease affects your patient, mark a vertical line on the scale for how well his or her condition is today."**

### **9.4.2 Physician's Global Assessment of Arthritis (PhGA-Arthritis)**

The Physician or delegate will assess how the subject's overall arthritis appears at the time of the visit. This is an evaluation based on the subject's disease signs, functional capacity, and physical examination using a 100mm VAS scale where 0 is "very good" and 100 is "very poor". The physician will be asked to mark the Patient's arthritis:

**The Patient's arthritis at this time is:**

**"Please mark a vertical line on the scale below to assess the overall status of the subject's arthritis signs and symptoms and the functional capacity of the subject."**

**Very Good-----Very Poor**

## **9.5 Patient's Assessment of Arthritis Pain (PtAAP)**

The PtAAP VAS or 'Pain VAS' is part of the ACR core set of measures in arthritis (Felson et al, 1993). Subjects will assess their arthritis pain using a VAS where 0 is "no pain" and 100 is "most severe pain."

---

## **9.6            Health Assessment Questionnaire-Disability Index score (HAQ-DI)**

The HAQ-DI contains 20 items divided into 8 domains that measure: dressing and grooming, arising, eating, walking, hygiene, reach, grip, and common daily activities. Subjects are required to indicate the degree of difficulty they have experienced in each domain in the past week on a 4-point scale that ranges from 0 (without difficulty) to 3 (unable to do). Any individual score of less than 2 is adjusted to 2 if the activity requires assistance from another individual or the use of an assistive device. The highest score in each category is then summed (0 to 24) and divided by the number of categories scored to give a score that ranges from 0 to 3.

## **9.7            High sensitivity C-reactive protein levels (hs-CRP)**

High sensitivity CRP levels will be analyzed by the central laboratory according to [Table 5-1](#).

After Baseline, the hs-CRP data will not be sent to the Investigator in order to protect the blinded nature of the treatment assignments and response.

## **9.8            Evaluation of psoriasis**

### **9.8.1            Body surface area-psoriasis (BSA-PSO)**

In the BSA-PSO assessment, the subject's hand (including the palm, fingers, and thumb) is used as the reference point for measuring how much of their skin is affected by PSO, representing roughly 1% of the body's surface.

The BSA palm method will be used for the evaluation of BSA affected by PSO as follows:

- Head and neck=10% (10 palms)
- Upper extremities=20% (20 palms)
- Trunk=30% (30 palms)
- Lower extremities=40% (40 palms)
- Total BSA=100%

### **9.8.2            Psoriasis Area and Severity Index (PASI)**

The PASI will be assessed in all subjects with Baseline/Day 1 BSA affected by PSO  $\geq 3\%$  determined by the method described in [Section 9.8.1](#) (ie, the BSA palm method).

The PASI is the most commonly used and validated assessment for grading the severity of PSO in clinical studies (Feldman, 2004). The PASI quantifies the severity and extent of the disease and weighs these with the percentage of BSA involvement.

The percent area of involvement (BSA%) is estimated across 4 body areas (head, upper limbs, trunk, and lower limbs) and then transferred into a grade ([Table 9-2](#)).

The Investigator assesses the average redness, thickness, and scaliness of lesions in each body area (each on a 5-point scale); 0=none, 1=slight, 2=moderate, 3=marked, and 4=very marked.

The PASI score ranges from 0 to 72 with a higher score indicating increased disease severity.

**Table 9-2: Body areas for calculation of percent BSA for PASI**

Body area	Details of area	BSA	Degree of involvement of body area a
Head	Face, back of head	10%	0 to 6
Upper limbs	Left, right, upper lower, flexor surface, extensor surface	20%	0 to 6
Trunk	Front, back, groin	30%	0 to 6
Lower limbs	Left, right, upper lower, flexor surface, extensor surface, including buttocks	40%	0 to 6
Total		100%	

BSA=body surface area; PASI=Psoriasis Area and Severity Index

a Where 0=none; 1=1% to <10% affected, 2=10% to <30% affected, 3=30% to <50% affected, 4=50% to <70% affected, 5=70% to <90% affected, 6=90% to 100% affected

The PASI75, PASI90, and PASI100 responses are based on at least 75%, 90%, and 100% improvement in the PASI score. The PASI will be assessed at Screening and at Baseline/Day 1. Thereafter, the PASI will be assessed for the purposes of determining response only in subjects with PSO involving at  $\geq 3\%$  of BSA at Baseline/Day 1.

### 9.8.3 Investigator's Global Assessment (IGA)

A static IGA for PSO will be used to assess disease severity in all subjects during the study. The IGA will be completed at the visits specified in [Table 5-1](#).

The Investigator will assess the overall severity of PSO using the following 5-point scale presented in [Table 9-3](#).

**Table 9-3: Five-point IGA**

Score	Short Descriptor	Detailed Descriptor
0	Clear	No signs of PSO; post-inflammatory hyperpigmentation may be present
1	Almost Clear	No thickening; normal to pink coloration; no to minimal focal scaling
2	Mild	Just detectable to mild thickening; pink to light red coloration; predominantly fine scaling
3	Moderate	Clearly distinguishable to moderate thickening; dull to bright red, moderate scaling
4	Severe	Severe thickening with hard edges; bright to deep dark red coloration; severe/coarse scaling covering almost all or all lesions

IGA=Investigator's Global Assessment; PSO=psoriasis

---

The IGA response is defined as a clear [0] or almost clear [1] assessment with at least a 2-category improvement from Baseline, meaning that this parameter will be evaluable only for subjects with psoriatic skin lesions (IGA score  $\geq 2$ ) at Baseline.

In this study, only subjects with BSA  $\geq 3\%$  at Baseline will have IGA assessed at post-Baseline Visits.

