### **4.2 Secondary variables**

#### **4.2.1 Secondary efficacy variables**

The secondary efficacy variables for this study are as follows:

- Change from Baseline in Health Assessment Questionnaire—Disability Index (HAQ-DI) at Week 16
- PASI90 response at Week 4 and Week 16 in the subgroup of subjects with PSO involving at least 3% BSA at Baseline
- Change from Baseline in the Short Form 36-item Health Survey (SF-36) Physical Component Summary (PCS) at Week 16
- Minimal Disease Activity (MDA) response at Week 16
- Change from Baseline in Van der Heijde modified Total Sharp Score (vdHmTSS) in subjects with elevated hs-CRP and/or at least 1 bone erosion at Baseline at Week 16
- Enthesitis-free state in the Leeds Enthesitis Index (LEI) at Week 16 in the subgroup of subjects with enthesitis at Baseline in the pooled population of PA0010 and PA0011
- Dactylitis-free state based on the Leeds Dactylitis Index (LDI) at Week 16 in the subgroup of subjects with dactylitis at Baseline in the pooled population of PA0010 and PA0011
- Change from Baseline in vdHmTSS in the overall population at Week 16

- ACR20 response at Week 16
- ACR70 response at Week 16
- Proportion of subjects with an Investigator Global Assessment (IGA) score of 0 (clear) or 1 (almost clear) AND at least a 2-grade reduction from Baseline at Week 4 and Week 16 in the subset of subjects with psoriatic skin lesions at Baseline
- Change from Baseline in the Patient's Assessment of Arthritis Pain (PtAAP) at Week 16
- Enthesitis-free state based on the Spondyloarthritis Research Consortium of Canada (SPARCC) index at Week 16 in the subgroup of subjects with enthesitis at Baseline
- Change from Baseline in Psoriatic Arthritis Impact of Disease-12 (PsAID-12) total score at Week 16

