**Table 5-1: Schedule of study assessments**

Protocol activity	Visit a / Week	Screening (V1) Baseline (Day 1) (first dose) (V2)	Double-Blind Treatment Period (weeks after first dose)										Active Treatment-Blind Period (weeks after first dose)																	
			3/ 2	4/ 4	5/ 6	6/ 8	7/ 10	8/ 12	9/ 14	10/ 16	11/ 18	12/ 20	13/ 22	14/ 24	15/ 26	16/ 28	17/ 30	18/ 32	19/ 34	20/ 36	21/ 38	22/ 40	23/ 42	24/ 44	25/ 46	26/ 48	27/ 50	28/ 52	ET	SFU b

k Includes evaluation of signs and symptoms of active TB and risk for exposure to TB.

l Any subject with PSO lesions at Baseline will have a BSA-PSO assessment (Section 9.8.1) at each scheduled visit.

m Only subjects with a BSA of  $\geq 3\%$  at Baseline will be required to have the PASI and IGA assessed at selected visits post Baseline (Day 1).

n Only for subjects who have nail PSO at Baseline.

o Circumference measured in millimeters.

p If a subject has had a radiograph of the chest within 3 months prior to the Screening Visit, it may be used as the Screening chest x-ray.

q The x-ray at Screening will be used for CASPAR classification (for inclusion) and will serve as the Baseline x-ray for assessment of the degree of joint damage, which will be assessed using the vdHmTSS (Van der Heijde et al, 2005).

r Adverse events are to be collected beginning at the signing of the Informed Consent form.

s The IXRS will be used to register subjects at Screening, to randomize eligible subjects to treatment groups at Baseline (Day 1), to reallocate subjects (at Week 16) in the placebo group, and to register visits.

[figure not shown]
t Bimekizumab subjects will be administered bimekizumab at Baseline, Week 4, and Q4W thereafter. The subjects will also receive dummy treatments at Week 2, and Q4W thereafter, in order to preserve the blind. Adalimumab subjects will be administered with adalimumab at Baseline, Week 2, and Q2W thereafter. Placebo will be administered at Baseline, Week 2, and Q2W thereafter to preserve blinding and correspond to the dosing schedule for adalimumab. For details of bimekizumab and adalimumab doses, see Section 7.2.

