## 14.7 Handling of dropouts or missing data

The primary method for assessing the efficacy variables will be the composite estimand approach to handling missing data that is similar to NRI. The sensitivity of results to the approach for handling missing data will be evaluated via supportive analyses using different missing data mechanisms.

In instances where MI is used, the missing value is replaced by a set of plausible values, where each value is a Bayesian draw from the conditional distribution of the missing data given the observed data. Intermittent missing data will be imputed using the MCMC method, followed by regression for monotone missing data. The multiple imputation procedures planned for efficacy analyses are based on an assumption of data missing at random (MAR).

Missing data will be evaluated as sensitivity analyses using different missing data mechanisms. The following sensitivity analyses for the primary efficacy variable will be conducted:

1. Multiple imputation as described above will be performed using the modified composite estimand. The definition of an intercurrent event is changed from all treatment discontinuation, to discontinuation of treatment due to AE or lack of efficacy.
2. A tipping point analysis will be performed to evaluate missingness assumptions. The tipping point analysis will be performed on the monotone missing data and only if the primary analysis is significant at  $\alpha=0.05$ . Various delta adjustments will be made to the assumed responses on the monotone missing data in each treatment group independently with various degrees of plausibility. It will include scenarios where subjects who have missing data and are randomized to bimekizumab have a lower probability of response compared to subjects who have missing data and were randomized to placebo. For binary variables, this includes the worst-case scenario where subjects who have missing data and are randomized to bimekizumab are considered nonresponders, while subjects who have missing data and were randomized to placebo are considered responders. The goal of the tipping point analysis is to systematically vary assumptions until there is no evidence of a treatment effect (if possible). The plausibility of such required delta adjustment will then be assessed. Details will be provided in the SAP.

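### The IGA 0/1 secondary endpoint has no BSA limit, but IGA is collected after Baseline only when BSA is at least 3%, so some subjects in its denominator would be nonresponders by design

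*Protocol*

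**What the plan says.** **Endpoint.** Protocol Section 4.2.1 lists IGA 0 or 1 with at least a 2-grade reduction "at Week 4 and Week 16 in the subset of subjects with psoriatic skin lesions at Baseline". Section 4.3.1 uses the same subset for the other visits. Section 9.8.3 treats lesions as a Baseline IGA of 2 or more, "meaning that this parameter will be evaluable only for subjects with psoriatic skin lesions". None of these places mentions BSA. The skin endpoint next to it does: "PASI90 response at Week 4 and Week 16 in the subgroup of subjects with PSO involving at least 3% BSA at Baseline".

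**Data collection.** The last sentence of Section 9.8.3 says that only subjects with BSA of at least 3% "at Baseline will have IGA assessed at post-Baseline Visits". Footnote m of Table 5-1 sets the same limit for PASI and IGA together. Two other places point the other way. Section 9.8.3 opens with "A static IGA for PSO will be used to assess disease severity in all subjects during the study". The Section 8 visit lists attach the 3% condition to PASI at each post-Baseline visit where it is scheduled, but list IGA with no condition.

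**Missing data.** Section 14.3.1.2 analyses secondary variables in all randomized subjects. Section 14.3.1.1 treats missing Week 16 data for the primary variable as nonresponse. Section 14.3.2 refers to NRI as the method already described for primary and secondary variables. Section 14.7 says: "The primary method for assessing the efficacy variables will be the composite estimand approach to handling missing data that is similar to NRI".

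**The concern.** The protocol fixes who is counted and who is measured, and the two groups differ. Subjects with a Baseline IGA of 2 or more and BSA below 3% meet the endpoint's definition, but the collection rule gives them no Week 4 or Week 16 value. If missing is set to nonresponse, they fail in every arm whatever the drug does. The reported response rates and the treatment difference for a listed secondary endpoint would then partly reflect a data-collection rule. Sites also have conflicting instructions, so whether a given subject below 3% BSA has IGA data may depend on which section the site follows.

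**Working it through.** **Can the affected group exist?** Table 9-3 grades thickening, colour and scaling, not extent. A small plaque can therefore score 2 or more in a subject with BSA below 3%.

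**Inputs**
- Planned arms: 420 bimekizumab, 280 placebo, 140 adalimumab (Section 14.9).
- Share of subjects with BSA of at least 3%: 60% (Section 14.9.2), which leaves 40% below.
- Response rates: none is given for IGA. Assumed stand-in: the PASI90 planning rates, 45% vs 10% (Section 14.9.2).
- q, the share of subjects below 3% BSA who have IGA of 2 or more: not given, so varied.
- r, the share of subjects with BSA of at least 3% who have IGA of 2 or more: not given, assumed 100% and then 80%.

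**The plan's own figure.** The protocol states no power for IGA. The nearest figure is the power above 99% for PASI90. With 0.60 × 420 = 252 and 0.60 × 280 = 168 subjects and 45% vs 10%, two-sided 5%, power exceeds 99.99%. With the continuity correction, 99% power needs 50 placebo subjects at this allocation, against 168 available. The stated figure reproduces.

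**Dilution.** The share of the IGA denominator that lacks post-Baseline IGA is

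s = 0.40q / (0.60r + 0.40q),

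and the observed rate is the true rate × (1 − s) in each arm. With r = 100%:

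| q | s | Bimekizumab | Placebo | Difference (points) | Odds ratio |
|---|---|---|---|---|---|
| 0% | 0% | 45.0% | 10.0% | 35.0 | 7.36 |
| 10% | 6.25% | 42.2% | 9.4% | 32.8 | 7.05 |
| 25% | 14.3% | 38.6% | 8.6% | 30.0 | 6.70 |
| 50% | 25% | 33.75% | 7.5% | 26.25 | 6.28 |
| 100% | 40% | 27.0% | 6.0% | 21.0 | 5.79 |

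Example, q = 50%: s = 0.20 / (0.60 + 0.20) = 0.25, so 0.45 × 0.75 = 33.75% and 0.10 × 0.75 = 7.5%.

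With r = 80% the difference is 32.3 points at q = 10%, 24.7 at q = 50% and 19.1 at q = 100%.

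**Numbers of subjects.** Up to 0.40 × 420 = 168, 0.40 × 280 = 112 and 0.40 × 140 = 56 subjects have BSA below 3%. At q = 50%, 84, 56 and 28 of them would be in the IGA denominator without a post-Baseline value.

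**Power.** It stays above 99% in every row. Both rates shrink by the same factor, so their ratio stays at 45/10 = 4.5.

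**The case against.** **NRI is not stated for IGA by name.** This stands. In Section 14.3.1.2, the sentence carrying the primary method to binary variables follows a list of hierarchy endpoints that does not include IGA. The rule in Section 14.3.1.1 concerns ACR50 at Week 16. NRI reaches IGA only through the general wording of Sections 14.3.2 and 14.7. But the protocol offers no other primary method for this endpoint, and nothing exempts values missing by design.

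**Section 9.8.3 can be read as setting both conditions.** Its two closing statements, taken together, suggest IGA of 2 or more and BSA of at least 3%. That may be the intention, and an SAP could apply it. However, Sections 4.2.1 and 4.3.1 define the population without the BSA limit, and an SAP restriction would change that definition. It would also leave the conflicting site instructions in place.

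**The opening of Section 9.8.3 may be a general statement that Table 5-1 then narrows.** This is fair, since IGA is listed for everyone at Screening and Baseline. The Section 8 post-Baseline lists are the harder conflict. They also mean that some subjects below 3% may be assessed in practice, which would reduce the dilution.

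**Stronger readings to avoid.** A reader might infer that everyone with lesions and low BSA becomes a failure, or that 40% of the denominator is affected. The first overlooks the IGA threshold of 2. The second needs nearly every subject below 3% BSA to meet that threshold, and inclusion criterion 7 admits subjects with only a history of psoriasis, who may have no lesions.

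**Conclusion.** The endpoint is wrong as written, with moderate consequences. Its definition and the collection rule are incompatible. Followed literally, they understate the response rates in all arms and the bimekizumab–placebo difference by the factor 1 − s. The protocol does not give s. The illustrative fall from 35 points to about 33, 26 or 21 rests on the PASI90 stand-in rates, 60% of subjects with BSA of at least 3%, all of those having IGA of 2 or more, and NRI applied to every unassessed subject in the denominator.

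It would be tempting to conclude that a formal test is at risk. The documents do not support that: IGA is outside the testing hierarchy, the dilution moves the difference towards zero and so does not inflate type I error, and power remains above 99% under these assumptions. The observed-case summary planned in Section 14.3.1.2 would drop the unassessed subjects. What is affected is the reported response rate and effect size.

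**What to change.** Before treatment codes are released at the Week 24 interim lock:
- In Sections 4.2.1, 4.3.1 and 9.8.3, define the IGA response subset as IGA of 2 or more and BSA of at least 3% at Baseline.
- In the opening of Section 9.8.3, limit the all-subjects statement to Screening and Baseline.
- In the Section 8 post-Baseline visit lists, add to IGA the BSA condition that PASI already carries.

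These are wording changes only. The cost is a smaller subset and an endpoint that speaks only to subjects with BSA of at least 3%, as PASI90 already does. The alternative, assessing IGA after Baseline in everyone with a Baseline IGA of 2 or more, keeps the wider population, but it adds assessments and cannot recover visits already passed. Settling the denominator after unblinding would make it post hoc.
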